13. RISKS AND DISCOMFORTS AND MINIMIZATION OF RISKS

Risk is the probability and magnitude of harm or discomfort anticipated as a result of participation in the research.

Minimal risk means the probability and magnitude of harm or discomfort anticipated in the research are not greater in and of themselves than those ordinarily encountered in daily life or during the performance of routine physical or psychological examinations or tests.

- a) Describe any risks of harm to subjects and/or anticipated discomfort(s) that are reasonably foreseeable, even if unlikely. Identify the safeguards you will put in place to minimize the occurrence of these risks and discomforts. Risks of harm and discomfort may include: physical harm/discomfort, psychological harm/discomfort, legal harm/discomfort, social harm/discomfort and economic harm.

Response: There are two methods of extubation in patients undergoing anesthesia: deep or awake. Currently, deep extubation is the default extubation method at MEE. However, in almost every other institution in the country, awake extubation is the default method. Risks of airway complications are associated with both methods and can include the following: 1) desaturation and hypoxia; 2) partial or complete laryngospasm; 3) bronchospasm; and 4) negative pressure pulmonary edema. Since this study is observational, there will be no risk for patients accruing from participating in the study. Recording of additional data by the anesthesiologist assigned to the case after extubation will not impact clinical care of the patient as the anesthesiologist will be monitoring the same vital signs whether the patient is part of the study or not. The computerized anesthesia manager program captures all the vital signs until the patient is disconnected and transported to the PACU. In the PACU, the data

recorder will be recording the additional data. The only document with the patient’s identifiers will be the data sheet, which will be filled out by the anesthesiologist during the case and by the data recorder in the PACU. Subsequently, all data will be recorded as a research record on an MEE password protected computer. Patient’s data sheets will be locked in the drawers located in the anesthesia office on the 7th floor of the MEE main building. Only the study coordinator and the principal investigator have access to these drawers. Consequently, the patients’ data will remain confidential all the time.

- b) If applicable, describe any group harms (i.e. research that focuses on a specific group or population that if the results are disclosed, could harm the group as a whole).

Response: N/A

- c) Describe any anticipated circumstances in which a “breach of confidentiality” associated with a mandated disclosure (e.g. reporting abuse to authorities) may occur as part of this study?

Response: N/A

- d) What risk classification (taking into consideration the probability and magnitude of harm) is appropriate for the proposed research?

Minimal Risk Greater than Minimal Risk Unknown

- e) Explain why you feel this category is appropriate based on the definition above (if more than minimal risk, describe the likelihood and seriousness of such risks).

Response: This study is an observational study; thus, there will be no intervention. The deep extubation is a method of extubation used for patients for any type of surgery. After transport to the PACU, the anesthesiologist routinely stays with the patient until it is safe to hand the patient off to a PACU nurse.

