7. RECRUITMENT PROCESS

NOTE: HIPAA does not permit non-MEE physicians to disclose patient information to Mass Eye and Ear for research recruitment. Non-MEE physicians may inform their patients of a research study and allow the patients to self-disclose their interest to the MEE study team.

Provide a detailed description of the recruitment plan (consistent with information you provide in the PRA), who is responsible for recruitment, how and when subjects will be recruited (i.e., flyers, advertisements, letters and oral/telephone scripts, email, at clinic appointments, etc.). Note: The HSC must review all recruitment materials. Please upload these materials into IRBNet with this submission.

Response: All adult patients who undergo head and neck surgery as well as deep extubation at the end of the surgery will be eligible for this study. The protected health information, including only names, MRN, and Date of surgeries of all eligible patients will be accessed from Epic at the screening process. We will not use email, fliers or brochures to recruit subjects. All surgeons performing head and neck surgery and all anesthesiologists at MEE will be notified of and informed about the study. Upon arrival to the preoperative area at MEE two hours prior to surgery, patients will be registered and seen by the preoperative nurse. Afterwards, an anesthesiologist will perform the preoperative evaluation. A data-recording form will be handed to the anesthesiologist in order to collect all the information requested in the form for patients undergoing deep extubation at the end of the surgery. The investigator and study coordinator will monitor the data collecting.

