9. STUDY PROCEDURES

- a) Provide a detailed description of all study procedures and intervention(s) each subject and/or cohort will experience. Provide a schedule of visits and the procedures that occur at each visit (e.g., tests, questionnaires, surveys, imaging or other interventions.). If the study also involves standard of care, differentiate between research only procedures and standard of care.

Response:

Preoperative Phase	
 • Research only: All surgeons who perform head and neck surgery at MEE will be notified of and informed about the study. • Upon arrival to the preoperative area at MEE two hours prior to surgery, patients will be registered and then seen by the preoperative nurse. • Next, an anesthesiologist will perform the preoperative evaluation. • Women aged 18 years and older will be offered a pregnancy test screening. • An IV catheter will be placed in all patients in the preoperative holding area on the surgical floor. • Research only: A data-recording form will be handed to the anesthesiologist. • Research only: The anesthesiologist will fill out data sheet questions related to patient’s past medical history from the anesthesia preoperative evaluation form. • Research only: The data-recording form will include multiple parameters that will be recorded in the perioperative period to quantify any adverse respiratory events including: 
 1. Oxygen saturation at the following intervals: 5 minutes prior to extubation; immediately before extubation; every minute for the first 10 minutes following extubation, except during transport to the PACU; and subsequently, every 5 minutes for the ensuing 30 minutes; 2. Endtidal CO₂ at the time of extubation; 3. Desaturation to less than 95% for more than 10 seconds; 4. Type and amount of opiates administered during the surgery; 5. Time from the end of the surgery to leaving the OR;
--------------------	---

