	
 6. Systolic and diastolic blood pressure and heart rate at the time of extubation, as well as upon arrival in the PACU, and subsequently, every 5 minutes for the first 30 minutes; 7. Episodes of persistent cough, defined as 3 or more consecutive coughs; 8. Episodes of complete or partial laryngospasm; 9. Episodes of bronchospasm; 10. Incidence of negative pressure pulmonary edema; 11. Incidence of vomiting; 12. Incidence and type of airway interventions; 13. Episodes of apnea; 14. Type and amount of opiates administered during the PACU stay; 15. Length of stay in minutes from admission to the PACU to discharge home; 16. Any unplanned hospital admissions due to perioperative respiratory adverse events;

Intraoperative Phase
	
 • Standard ASA monitors, including pulse-oximetry, ECG, non-invasive blood pressure, thermometer, and capnography, will be applied in all patients. • All patients will be preoxygenated prior to induction. • Induction: 
 ○ The choice of induction drugs will be at the discretion of the anesthesiologist. • Maintenance: 
 ○ The choice of maintenance drugs, including choice and dose of opiates, will be at the discretion of the anesthesiologist. • Emergence and extubation: 
 ○ The choice extubation method (deep vs awake) will be at the discretion of the anesthesiologist.

	
 ○ Deep extubation criteria will be at the discretion of the anesthesiologist. ○ An oral or nasal airway will be placed in patients immediately after deep extubation.
Postoperative Phase	
 ● All patients will be transported to the post-anesthesia care unit (PACU) with a facemask receiving oxygen. ● The anesthesiologist will remain with the patient until he/she is stable enough to be handed off to the PACU nurse. ● Patients will be continued on supplemental oxygen until fully awake; they will be placed on room air when able to maintain adequate oxygen saturation as assessed by the PACU nurse. ● Research only: The data-recording form will be handed to data recorder in the PACU to be completed.
Discharge	Patients will be discharged home or to the floor after meeting PACU discharge criteria.
Analysis	Research only: The data will be analyzed and reported.

b) 9b. Describe any data and/or sample banking, if applicable.

Response: N/A

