10. STUDY OUTCOMES

- a) **Primary Outcome Measure(s)** - describe how you will measure the primary and other outcomes of the study (e.g., blood pressure change, changes in visual acuity using a specific test, pain scales, responses on a questionnaire, etc.). Upload copies of your data collection tools and/or a list of all variables/data points you will collect.

Note: Primary outcome measures may be measured in various ways such as:

- binary (e.g. improvement in symptoms vs. no improvement in symptoms)
- continuous (e.g. weight - kg, blood loss - mL)
- ordinal (e.g. pain - mild, moderate, severe)
- time to event (e.g. survival)
- counts (e.g. number of infections, number of events occurring)

Response:

Primary outcome measures include:

- 1) **Desaturation to less than 95% for more than 10 seconds;**
- 2) **Episodes of persistent cough, defined as 3 or more consecutive coughs;**
- 3) **Episodes of complete or partial laryngospasm;**
- 4) **Episodes of bronchospasm;**
- 5) **Incidence of negative pressure pulmonary edema;**
- 6) **Obstruction that requires maneuvers, oral airway or jaw thrust**

- b) Describe any secondary or other outcomes (exploratory):

Secondary outcome measures include:

- 1) **Length of time from end of surgery to leaving the operating room;**
- 2) **Length of stay from admission to and discharge from the PACU Stage 1 and 2;**
- 3) **Incidence of unexpected hospital stay related to perioperative respiratory complications.**
- 4) **Incidence of sore throat**

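### In the OR, desaturation (primary outcome 1) is written on a form by the treating anesthesiologist, and the automated vital-sign record the plan describes is neither its source nor a check on it

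*Combined protocol and SAP*

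**What the plan says.** Section 10 a) lists as its first primary outcome "Desaturation to less than 95% for more than 10 seconds". In Section 9 a) the same event is item 3 of the data-recording form. Item 1 of that form separately asks for saturation values before extubation and then "every minute for the first 10 minutes following extubation, except during transport to the PACU; and subsequently, every 5 minutes for the ensuing 30 minutes".

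On who records, Section 7 says "A data-recording form will be handed to the anesthesiologist in order to collect all the information requested in the form". Section 13 a) describes the data sheet as one "which will be filled out by the anesthesiologist during the case and by the data recorder in the PACU". On who decides, Section 9 a) says "The choice extubation method (deep vs awake) will be at the discretion of the anesthesiologist", and it leaves the criteria for deep extubation to the same person.

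On what else is available, Section 13 a) states "The computerized anesthesia manager program captures all the vital signs until the patient is disconnected and transported to the PACU". Section 19 a) repeats the statement. In both places it supports the argument that the study adds no risk. Oversight of the data is general: the investigator and coordinator monitor collection (Section 7), and the coordinator reviews and compiles the data (Section 20 b).

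**The concern.** Of the six primary outcomes, desaturation is the one a monitor measures directly, so it could be ascertained without judgement. As planned, its OR component depends on one clinician noticing a short event, timing it and writing it down just after extubation. That clinician is also placing an oral or nasal airway and is asked to note cough, laryngospasm, bronchospasm, apnea and airway interventions. The same clinician chose the technique whose complications are being counted.

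The study's only aim is to estimate complication rates. Events that go unrecorded lower the estimate, and enrolling more patients does not repair that. It would also carry into the comparison with other institutions in Section 11. The plan describes a record made independently of the observer but gives it no role in the outcome.

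**Working it through.** **1. The plan's own figure.** Section 12 gives 95% confidence interval half-widths of 5% at a 30% rate and 6% at a 35% rate, with n = 300. The simple formula is 1.96 × √(p(1−p)/n):
- p = 0.30: 1.96 × √(0.30 × 0.70/300) = 5.19 points.
- p = 0.35: 1.96 × √(0.35 × 0.65/300) = 5.40 points.

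The exact (Clopper-Pearson) half-widths are 5.33 and 5.54 points, which round to the stated 5 and 6. The figures reproduce and are not in dispute. The formula contains only p and n, so it describes sampling error and says nothing about events that were never recorded.

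**2. Who records desaturation, and what could verify it, by location.**

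| Location | Who completes the form | Automated record described? | Given a role in the outcome? |
|---|---|---|---|
| OR, extubation to disconnection | Treating anesthesiologist | Yes (Sections 13 a, 19 a) | No |
| Transport | Not stated; timed readings are excepted | No, capture ends at disconnection | No |
| PACU | Data recorder | None described | No |

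The point is confined to the first row. Only there does the plan describe an objective record and leave it unused.

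**3. Can the timed readings on the form verify item 3?** Not for short events. Readings are one minute apart at best, and an event of little more than 10 seconds can lie wholly between two of them. The same person also writes both items, so agreement between them would not be independent.

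**4. Can the automated record verify item 3?** That depends on its storage interval, s seconds, which the documents do not give. An event just over 10 seconds is certain to contain a stored value only if s is 10 or less. Showing from stored values that it lasted more than 10 seconds takes several consecutive low values, so s must be shorter still. A coarser record could still expose longer events missing from the form, but could not replace item 3.

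**5. Can the bias be sized?** The expected recorded rate is

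true rate × sensitivity + (1 − true rate) × false-positive rate.

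For OR desaturation, none of the three inputs is in the documents. The 30% in Section 12 is used there as an overall respiratory complication rate. No magnitude can be derived.

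**The case against.** The strongest reply is that item 3 is an event item, distinct from the timed readings. An attentive anesthesiologist watching a pulse oximeter can record an event that falls between readings, and nothing shows that events are missed. That stands: the supported statement is that they may be under-recorded. A reader might go further and divide event length by reading interval, getting 10/60 = 17%, 20/60 = 33% and 30/60 = 50% for events of 10, 20 and 30 seconds. Those would be detection rates only if the outcome were scored from the timed readings, and the plan does not score it that way.

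A reader might also take the 30% in Section 12, suppose that a fifth of events go unrecorded, and infer 0.30 × 0.80 = 24%, a 6-point loss that exceeds the 5-point half-width. The documents do not support this. The loss is invented and the 30% is not a desaturation rate. If it means any complication, a patient whose OR desaturation is missed still counts through cough, laryngospasm, obstruction or a PACU event.

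The automated record is also not shown to be better. If it stores one value per minute, it has the same blind spot as the timed readings. This stands, and it is why the fix is conditional on the storage interval.

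The sentence about automated capture is followed directly by one on the PACU data recorder, so the pair could be read as describing where data come from in each place. On that reading the OR source is unspecified rather than excluded. The remedy is unchanged, because the plan would still have to name the source.

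Finally, deep extubation is the institutional default, which weakens any suggestion of personal interest. That is fair. The point needs no motive: a busy single observer without verification is enough.

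**Conclusion.** The point holds as a gap in how one primary outcome is ascertained in one location. In the OR, desaturation is recorded by hand by the clinician who chose the technique. The plan says vital signs there are captured automatically, and it uses that capture neither as source nor as check. Under-recording is possible and would go undetected.

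The documents do not show that events are in fact missed, do not establish how many, and do not show that the stored record can resolve a 10-second event. No numerical bias should be quoted. This is a cheap improvement to measurement. It changes neither the sample size nor the confidence level, and it does not invalidate the design. It rests on taking Sections 13 a) and 19 a) at their word that saturation is among the vital signs captured until disconnection.

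**What to change.** In Sections 9 a) and 10 a):

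- State that, for every patient, the study coordinator extracts the automated saturation record from extubation to disconnection under one fixed written rule. The rule should say how many consecutive stored values define an event and how probe-off artefact is screened.
- State the record's storage interval.
- If the interval can resolve a 10-second event, name the record as the primary source for OR desaturation, with form item 3 as the supplement. If it cannot, keep item 3 as the source and use the record as a cross-check. Settle this before data are examined.
- In both cases, report how often the two sources disagree. Report the rate counting an event from either source as a sensitivity analysis only, since that rule can only raise the count and may admit artefact.
- State as a limitation that transport and the PACU have no automated source in the plan, so ascertainment differs by location.

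The cost is modest extraction work on about 300 existing records, by a coordinator who already reviews the data, plus some residual artefact. Patient care and enrollment are unaffected.

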14. ALTERNATIVES

Describe any alternatives, to research participation available to potential patients.

Note: If there are no alternatives, other than “not participate” state so.

Response: N/A

15. BENEFITS

- a) Will individual subjects have any direct benefits from the research? If subjects will not experience direct benefit, state so.

Response: Subjects will not receive any direct benefits.

- b) Explain the potential benefits to science, and/or society as a result of this research.

Response: As deep extubation is the default method at MEEI, our study might be able to illustrate and elucidate the safety features as well as the rate of different respiratory complications of the deep extubation in adult patients undergoing head and neck surgery.

- c) If this study is more than minimal risk, explain how the risks are minimized in relation to the anticipated benefits of the study:

Response: N/A

16. DISSEMINATION OF RESULTS

- a) Describe any plans to share research results with subjects, EITHER individual results and/or aggregate results. If there are no plans to share results, explain why this is not feasible, appropriate, or applicable to this research.

Response: N/A – This study is exempt from obtaining consent from patients as the nature of this study is observational and we collect very minimal patient identifiers. Also, all patients' data being collected and analyzed in this study are de-identified.

- b) How will results be published, and in what form (newsletter to subjects, peer-reviewed publications)?

Response: The results of this study will be published on peer-reviewed medical journals. Subjects will not be individually identifiable in publications.

17. INCIDENTAL FINDINGS

If there is the possibility that study procedures may identify incidental findings of medical importance to a subject and/or the subject's family (e.g., genetic studies, imaging studies, studies that conduct routine blood tests, etc.), describe the plan for reporting any incidental findings (e.g., study physician will discuss with subject/subject's PCP, genetic counseling). In addition, researchers may uncover evidence of child, domestic, or elder abuse, which require reporting to authorities. Please describe the plan for reporting such findings.

Response: There will not be a possibility of clinically significant incidental findings being discovered during research procedures as this study is clinical research

18. PRIVACY/CONFIDENTIALITY

NOTE: MEE researchers must adhere to MEE Information Security Policies and Procedures when designing their research protocols. The HSC evaluates the collection, use and storage of data and may require additional safeguards. For example, the HSC may require a Certificate of Confidentiality for research projects that collect personally identifiable, sensitive information.

- a) Describe the plan for protecting the privacy and confidentiality of subjects throughout the research (e.g., limited access to medical records and identifiable study data, data security procedures consistent with MEE Information Security Policy).

Response: Research data will be coded using a subject identification number that does not include the subject's initials and is not derived from the subject's identifiable information. The key linking the subject identification number to the subject's identifiable information (only MRN) is available only to Mass. Eye and Ear PI and other MEE study team members.

- b) Where will you store research data, signed informed consent forms, and assent forms to maximally protect privacy and confidentiality?

Response: Response: Paper files will be locked in cabinets when not in use and protected from inappropriate access. Electronic data will be stored in a password protected file and networked MEE computer for which access is limited to authorized members of the study team only.

- c) Please provide the plan for destroying identifiers (at the earliest opportunity as consistent with the research plan) or provide a health or research justification for retaining identifiers. For protocols subject to future and secondary data analysis, provide justification for not destroying identifiers permanently and explain plans for future use (i.e., establishment of a data or specimen repository).

Response: Identifiers will be destroyed after the publication of the study

- d) Will you obtain samples/data from outside sources? Please specify from whom you will obtain samples and what information you will obtain with each sample. Please note that a Material Transfer Agreement may be required for this research activity. (Contact Research Administration for instructions.)

Response: No

- e) Will samples from MEE be provided to outside sources? Please specify to whom you will provide MEE samples and what information/data will accompany each sample. Please note that that a Material Transfer Agreement will be required for this research activity.

Response: No

19. DATA and SAFETY MONITORING PLAN (DSMP)

- a) If the research is no more than minimal risk, describe any provisions in place to ensure the safety of participants. In minimal risk studies, there is always the risk of loss of confidentiality and privacy. However, minimal risk studies involving blood draws, imaging, and eye exams may have risks associated with the study procedure.

Response: Risks of airway complications are associated with both awake and deep extubation methods and can include the following: 1) desaturation and hypoxia; 2) partial or complete laryngospasm; 3) bronchospasm; and 4) negative pressure pulmonary edema. Since this study is observational, there will be no risk for patients accruing from participating in the study. Recording of additional data by the anesthesiologist assigned to the case after extubation will not impact clinical care of the patient as the anesthesiologist will be monitoring the same vital signs whether the patient is part of the study or not. The computerized anesthesia manager program captures all the vital signs until the patient is disconnected and transported to the PACU. In the PACU, the data recorder will be recording the additional data. The only document with the patient's identifiers will be the data sheet, which will be filled out by the anesthesiologist during the case and by the data recorder in the PACU. Subsequently, all data will be recorded as a research record on an MEE password protected computer. Patient's data sheets will be locked in the drawers located in the anesthesia office on the 7th floor of the MEEI main building. Only the study coordinator and the principal investigator have access to these drawers. Consequently, the patients' data will remain confidential all the time.

- b) If the research is more than minimal risk, please provide a detailed data and safety monitoring plan (DSMP). Include the individual(s) or group responsible for data and safety monitoring (e.g., PI, specific members of the study team, independent monitor(s), a convened Data and Safety Monitoring Board - DSMB) Please see the guidance document in IRBNet for developing a DSMP.

Response: N/A

- c) Provide information related to the expertise and qualifications of the individual(s) and/or groups listed above relative to monitoring.

Response: N/A

- d) Please explain how data and safety monitoring activities for this study will be documented (e.g., a monitoring log kept in the regulatory binder).

Response: N/A

- e) Explain if any individual involved in monitoring has relationships with sponsors, organizers or researchers, conducting the study, and if applicable, describe the nature of these relationships.

Response: N/A

- f) If applicable, describe the process for communication of Data and Safety Monitoring Board reports to the investigator and to the HSC.

Response: N/A

